4.4. Duration of Treatment and Subject Participation

After signing the ICF, screening assessments may be completed over a period of up to 28 days. Each subject enrolled in the study may continue to receive study treatment until treatment discontinuation criteria are met. If the subject discontinues all study treatment (INCB039110 and ibrutinib), then the treatment period will end, and the subject will enter the follow-up period (see Section 6.4). Study participation is expected to average approximately 6 months per individual subject.

4.5. Overall Study Duration

The study begins when the first subject signs the ICF. The end of Phase 1 will occur when all subjects have completed the DLT surveillance period; Phase 2 will end once the last subject is assessed for response.

Once the last subject is evaluable for response, a database lock of the study will occur to allow the analysis of the study data. Any remaining subjects may continue to receive study treatment and be seen by the investigator per usual standard of care for this population. Provisions will be made to ensure access to treatment for subjects who are continuing to benefit from study treatment at the time of study termination.

The investigator will be expected to monitor for and report any SAEs, AEs of special interest, and pregnancies, as detailed in Section 8. The remaining subjects are considered to be on study until a discontinuation criterion is met and written notification is provided to the sponsor.

The study will end once all subjects have discontinued study treatment and safety follow-up.

4.6. Study Termination

The investigator retains the right to terminate study participation at any time, according to the terms specified in the study contract. The investigator is to notify the institutional review board (IRB)/independent ethics committee (IEC) in writing of the study's completion or early termination, send a copy of the notification to the sponsor or sponsor's designee, and retain 1 copy for the site study regulatory file.

The sponsor may terminate the study electively due to ethical concerns, insufficient subject recruitment, alterations in accepted clinical practice, emerging data, or if required by regulatory decision. If the study is terminated prematurely, then the sponsor will notify the investigators, the IRBs and IECs, and regulatory bodies of the decision and reason for termination of the study.

5. TREATMENT

5.1. Treatment Assignment

5.1.1. Subject Numbering and Treatment Assignment

Study sites will enter subject demographic and baseline data into the interactive voice response system (IVRS) in order to receive a subject number and treatment allocation.

All subject numbers will be 6 digits; the first 3 digits will be the site number, and the last 3 digits will be the subject's number. This subject number will be maintained throughout the study and will not be reassigned. Subjects who withdraw consent or discontinue from the study after being assigned a subject number will retain their initial number.

Site staff will contact the IVRS to allocate the subject to treatment assignment and obtain the initial study drug assignment. The investigator or designee will select the assigned bottles of study drug from their stock that correspond to the number provided by the IVRS and dispense the study drug to the subject. All subsequent dispensing of study drug should follow this process. Refer to the IVRS manual for detailed information.

If a subject is mistakenly given a bottle of study drug that is not the bottle assigned by the IVRS, then the IVRS help desk must be notified immediately. The reason for the misallocation of the study drug must be documented by the study site and reported to the IRB/IEC.

For subjects who signed an ICF but are not allocated study drug and for subjects who are allocated study drug but were not treated, refer to the electronic case report form (eCRF) Completion Guidelines for instruction on which eCRFs to complete.

5.1.2. Randomization and Blinding

[figure not shown]
Not applicable.

5.2. INCB039110

5.2.1. Description and Administration

INCB039110 drug substance is a white to off-white powder. INCB039110 100 mg (free base equivalent) sustained release tablets (SR3 formulation) contain the active ingredient, hypromellose, microcrystalline cellulose, lactose monohydrate, and magnesium stearate.

In Phase 1, INCB039110 tablets will be administered orally (PO) at the cohort-specific dose (eg, 3 × 100 mg tablets) QD. In Phase 2, INCB039110 tablets will be administered PO at the RP2D identified in Phase 1. The use of strong CYP3A inhibitors/inducers, grapefruit, and pomegranate should be avoided for the duration of the study ([Appendix B](#)).

Due to the potential for WBC margination, blood samples should be collected before study treatment administration at all applicable study visits.

Subjects may have dose reductions of INCB039110 during the course of treatment based on AEs, clinical evaluation, and laboratory assessments. See Section [5.5.1](#) for INCB039110 dose modification guidance.

Subjects are permitted to remain on INCB039110 until withdrawal from study treatment is considered necessary as per Section [5.6](#).

5.2.2. Supply, Packaging, and Labeling

INCB039110 will be provided to sites as 100 mg tablets packaged in high-density polyethylene bottles as applicable by Incyte. No preparation is required.

All Incyte investigational product labels will be in the local language and will comply with the legal requirements of each country.

5.2.3. Storage

INCB039110 should be stored at ambient conditions (15°C to 30°C, or 59°F to 86°F) as per the [IB](#).

5.2.4. Instruction to Subjects for Handling INCB039110

The subject must be instructed in the handling of INCB039110 as follows:

- Store the study medication at room temperature.
- Remove only the number of tablets from the study drug bottle needed at the time of administration.
- Do not remove doses in advance of the next scheduled administration.
- Make every effort to take doses on schedule.
- Report any missed doses.

5.3.4. Instruction to Subjects for Handling Ibrutinib

The subject must be instructed in the handling of ibrutinib as follows:

- Store the study medication in accordance with the manufacturer's storage conditions.
 - Remove only the number of tablets from the study drug bottle needed at the time of administration.
 - Do not remove doses in advance of the next scheduled administration.
 - Make every effort to take doses on schedule.
 - Report any missed doses.
 - Take study medication with a glass of water.
 - Do not open capsules nor dissolve them in water.
 - Do not take another dose if vomiting occurs after taking study medication.
 - If a dose of ibrutinib is not taken at the scheduled time, it should be taken as soon as possible on the same day with a return to the normal schedule the following day.
 - The subject should not take extra capsules to make up the missed dose.
- █ [REDACTED]
- Keep study drug in a safe place and out of reach of children.
 - Bring all used and unused ibrutinib kits to the site at each visit.

5.3.5. Overdose

Any dose of ibrutinib in excess of that specified in this Protocol is considered to be an overdose. Signs and symptoms of an overdose that meet any SAE criterion must be reported as a SAE in the appropriate timeframe and documented as clinical sequelae to an overdose. There is no specific experience in the management of ibrutinib overdose in patients. No maximum tolerated dose was reached in the Phase 1 study in which subjects received up to 12.5 mg/kg per day (1400 mg/day). Healthy subjects were exposed up to a single dose of 1680 mg. One healthy subject experienced reversible Grade 4 hepatic enzyme increases (AST and ALT) after a dose of 1680 mg. Subjects who ingested more than the recommended dosage should be closely monitored and given appropriate supportive treatment.

5.4. Treatment Compliance

Compliance with all study-related treatments should be emphasized to the subject by the site personnel, and appropriate steps should be taken to optimize compliance during the study. Compliance with INCB039110 and ibrutinib will be calculated by the sponsor based on the drug accountability documented by the site staff and monitored by the sponsor/designee (tablet counts). Subjects will be instructed to bring all study drugs with them to the study visits in order for site personnel to conduct tablet counts to assess study drug accountability. The drug accountability documentation will be used by the sponsor to calculate treatment compliance.

5.5. Treatment Interruptions and Adjustments

5.5.1. Dose Modifications

5.5.1.1. Dose Modification of INCB039110

Treatment with INCB039110 may be delayed up to 2 weeks (14 days) to allow for resolution of toxicity. Subjects may resume treatment if no medical condition or other circumstance exists that, in the opinion of the investigator, would make the subject unsuitable for further participation in the study. The treating investigator should contact the sponsor to discuss the case of any subject whose treatment has been delayed for more than 14 days before restarting treatment with INCB039110.

Because subjects may enter the study with extensive pretreatment and/or severe bone marrow infiltration by the primary disease, dose interruption and reduction rules are provided as guidelines (see Table 4 and Table 5). Individual decisions regarding dose reduction should be made using clinical judgment and in consultation with the sponsor's medical monitor, taking into account relatedness of the AE to the study drug and the subject's underlying condition. Adverse events that have a clear alternative explanation or transient (≤ 72 hours) abnormal laboratory values without associated clinically significant signs or symptoms may be exempt from dose-reduction rules.

Table 4: Guidelines for Interruption and Restarting Study Drug

ADVERSE EVENT	ACTION TAKEN
Chemistry	

 • AST and/or ALT $> 3.0 \times \text{ULN}$ Note: In subjects with bone metastasis-related elevations at baseline, contact sponsor to discuss clinical management and possible dose reductions.	
Step 1: Interrupt INCB039110 up to 14 days until the toxicity has resolved to \leq Grade 1 (unless approved otherwise by the medical monitor).
 
Step 2: Restart INCB039110 at same dose. If assessed as related to INCB039110, restart at next lower dose. Monitor as clinically indicated.

Hematology	

 • ANC $\leq 1.0 \times 10^9/\text{L}$ unless due to underlying disease • Platelet count is $< 60 \times 10^9/\text{L}$ unless due to underlying disease 	
Step 1: Interrupt INCB039110 up to 14 days until the toxicity has resolved to \leq Grade 1 or pretherapy baseline.
 
Step 2: Restart INCB039110 at same dose; monitor as clinically indicated.


 • Grade 4 ANC ($< 0.5 \times 10^9/\text{L}$) • \geq Grade 3 ANC with an oral temperature of at least 38.5°C OR with \geq Grade 3 infection. • Platelet count is $< 35 \times 10^9/\text{L}$ 	
Step 1: Interrupt INCB039110 up to 14 days until the toxicity has resolved to \leq Grade 1.
 
Step 2: Restart INCB039110 at same dose. If assessed as related to INCB039110, restart at next lower dose. Monitor as clinically indicated.

Table 4: Guidelines for Interruption and Restarting Study Drug (Continued)

ADVERSE EVENT	ACTION TAKEN
Other toxicities	

 Any Grade 1 or Grade 2 toxicity 	Continue study treatment and treat the toxicity; monitor as clinically indicated.

 Any Grade 3 toxicity, if clinically significant and not manageable by supportive care 	
Step 1: Interrupt INCB039110 up to 14 days until the toxicity has resolved to \leq Grade 1.
 
Step 2: Restart INCB039110 at same dose. If assessed as related to INCB039110, restart at next lower dose. Monitor as clinically indicated.

 Any recurrent Grade 3 toxicity after 2 dose reductions 	Discontinue study drug administration and follow-up per Protocol. Exceptions require approval of sponsor.

 Any other Grade 4 toxicity 	Discontinue study drug administration and follow-up per Protocol. Exceptions require approval of sponsor.

Table 5: Dose Reduction Levels for INCB039110

Current Dose	First Dose Reduction	Second Dose Reduction
300 mg QD	200 mg QD	Discontinue
400 mg QD	300 mg QD	200 mg QD
200 mg QD	Discontinue	Discontinue

5.5.1.2. Dose Modification for Ibrutinib

The dose of ibrutinib should be modified according to the dose modification guidelines in [Table 6](#) if any of the following toxicities occur:

- Grade 4 ANC ($< 0.5 \times 10^9/L$) for more than 7 days.
- Grade 3 thrombocytopenia ($< 50 \times 10^9/L$) in the presence of clinically significant bleeding events.
- Grade 4 thrombocytopenia ($< 25 \times 10^9/L$).
- Grade 3 or 4 nausea, vomiting, or diarrhea if persistent, despite optimal antiemetic and/or antidiarrheal therapy.
- Any other Grade 4 or unmanageable Grade 3 toxicity.

For Grade 3 or 4 atrial fibrillation or persistent atrial fibrillation of any grade, the risks and benefits of ibrutinib treatment should be considered.

Ibrutinib is metabolized in the liver. For subjects who develop mild liver impairment while on study (Child-Pugh Class A), the recommended dose reduction for ibrutinib is to a level of 280 mg daily (2 capsules). For subjects who develop moderate liver impairment while on study (Child-Pugh Class B), the recommended dose reduction is to a level of 140 mg daily (1 capsule). Subjects who develop severe hepatic impairment (Child-Pugh Class C) must withhold study drug

until resolved to moderate impairment (Child-Pugh Class B) or better and could be re-treated according to resolved hepatic conditions (ie, 140 mg or 280 mg for moderate or mild impairment, respectively). Subjects should be monitored for signs of toxicity and follow dose modification guidance as needed.

If the dose of ibrutinib is reduced, at the investigator's discretion, the dose of ibrutinib may be re-escalated after 56 days of a dose reduction in the absence of a recurrence of the toxicity that led to the reduction. Dose changes must be recorded in the appropriate eCRF.

Table 6: Dose Modifications for Ibrutinib

Toxicity Occurrence	Action to be Taken
First	Withhold study drug until recovery to Grade \leq 1 or baseline; may restart at original dose level.
Second	Withhold study drug until recovery to Grade \leq 1 or baseline; may restart at 1 dose level lower (ie, 280 mg/day for 420 mg/day dose; 420 mg/day for 560 mg/day dose).
Third	Withhold study drug until recovery to Grade \leq 1 or baseline; may restart at 1 dose level lower (ie, 140 mg/day for 420 mg/day dose; 280 mg/day for 560 mg/day dose).
Fourth	Discontinue study drug.

5.5.2. Dose-Limiting Toxicity and Determination of Recommended Phase 2 Dose

A DLT will be defined as the occurrence of any toxicities in [Table 7](#) occurring up to and including Study Day 28, except those with a clear alternative explanation (eg, disease progression) or transient (\leq 72 hours) abnormal laboratory values without associated clinically significant signs or symptoms based on investigator determination. All DLTs will be assessed by the investigator using CTCAE v4.03 criteria ([NCI 2010](#)). In order to be included in the tolerability review, subjects must have received the cohort-specific dose of INCB039110 and ibrutinib for at least 75% of the days during the 28-day surveillance period or have experienced a DLT. Additional subjects may be enrolled to achieve a minimum cohort size should withdrawal or dose interruptions/reductions result in subjects being nonevaluable.

Individual subject dose reductions may be made based on events observed at any time during treatment with study drug; however, for the purposes of dose cohort escalation/de-escalation, expanding a dose cohort, and determining the RP2D, decisions will be made based on events that are observed from the first day of study drug administration through and including Day 28. A lower RP2D may subsequently be determined based on relevant toxicities that become evident after Day 28.

Table 7: Criteria for Defining Dose-Limiting Toxicity

Toxicity
Nonhematologic

 • Any \geq Grade 3 nonhematologic toxicity, EXCEPT the following: 
 – Transient (\leq 72 hours) abnormal laboratory values without associated clinically significant signs or symptoms. – Nausea, vomiting, and diarrhea adequately controlled with medical therapy within 48 hours. – Singular or nonfasting elevations in blood glucose (ie, blood glucose excursions will be considered toxicities if fasting blood glucose is elevated on 2 separate sequential occasions).
Hematologic

 • Grade 3 thrombocytopenia with bleeding. • Grade 4 thrombocytopenia. • Febrile neutropenia (ANC $<$ $1.0 \times 10^9/L$ and fever $>$ $101^\circ F/38.5^\circ C$). • Grade 4 neutropenia that does not recover to \leq Grade 2 in \leq 3 days after interrupting study drug. • Grade 4 anemia unresponsive to treatment. 
Note: "INCB039110 is suspected to cause transient decreases in ANC as a result of margination; therefore, DLT rules require neutropenia to persist after holding INCB039110 for 2 to 3 days. If the clinical status of the subject allows, investigators are encouraged to wait 24 hours before starting growth factors, to determine if WBC margination is contributing to the degree of neutropenia."

5.5.2.1. Management of Dose-Limiting Toxicities or Other Urgent Situations

In all cases, investigators may employ any measures or concomitant medications necessary to optimally treat the subject following discussion with the sponsor whenever possible.

5.5.2.2. Follow-Up of Dose-Limiting Toxicities

Any DLT should be followed until it resolves to baseline or Grade 1 or appears to have stabilized for a minimum of 4 weeks. During follow-up, subjects should be seen as often as medically indicated to assure safety.

5.6. Withdrawal of Subjects From Study Treatment

The decision to discontinue study treatment (eg, INCB039110 and ibrutinib) will not constitute study completion (see Section 5.6). In the event that the decision is made to discontinue study treatment, the treatment phase will be considered complete and the follow-up phase will begin.

5.6.1. Withdrawal Criteria

Subjects **must** be withdrawn from study treatment (INCB039110 and ibrutinib) for the following reasons:

- The subject has experienced an unacceptable toxicity.
- The subject is unable to tolerate INCB039110 at a dose of 200 mg QD.
- There is evidence of disease progression from radiographic tumor assessment.

- Further participation would be injurious to the subject's health or well-being, in the investigator's medical judgment.
- The subject becomes pregnant.
- Consent is withdrawn.
- The study is terminated by the sponsor.
- The study is terminated by the local health authority or IRB or IEC.

A subject **may** be withdrawn from study treatment in the following situations:

- If a subject is found not to have met eligibility criteria, then the medical monitor and investigator will collaborate to determine whether the subject should be withdrawn from the study.
- If a subject is noncompliant with study procedures or study drug administration in the opinion of the investigator, then the sponsor should be consulted for instruction on handling the subject.

5.6.2. Withdrawal Procedures

In the event that the decision is made to permanently discontinue study treatment, the subject will be withdrawn from the study, and the end-of-treatment (EOT) visit should be conducted. Reasonable efforts should be made to have the subject return for a follow-up visit as described in Section 6.

Subjects who discontinue study treatment for reasons other than disease progression will be assessed per standard of care until disease progression, initiation of new anticancer treatment, or death, whichever occurs first.

If a subject is withdrawn from study treatment:

- The study monitor or sponsor must be notified.
- The reason(s) for withdrawal must be documented in the subject's medical record and in the eCRF.
- The EOT visit should be performed.
- Subjects must be followed for safety until the time of the follow-up visit or until study drug–related toxicities resolve, return to baseline, or are deemed irreversible, whichever is longer.

5.7. Concomitant Medications

All concomitant medications and treatments must be recorded in the eCRF. Any prior medication received up to 30 days before enrollment will be recorded in the eCRF. Concomitant treatments and/or procedures that are required to manage a subject's medical condition during the study will also be recorded in the eCRF.

Supportive medications in accordance with standard practice (such as for emesis, diarrhea, etc.) are permitted. Use of neutrophil growth factors (filgrastim and pegfilgrastim) or red blood cell growth factors (erythropoietin) is permitted per institutional policy and in accordance with the

American Society of Clinical Oncology guidelines ([Smith et al 2015](#)). Transfusions may be given in accordance with institutional policy.

Short courses (≤ 14 days) of steroid treatment for non-cancer related medical reasons (eg, joint inflammation, asthma exacerbation, rash, antiemetic use, infusion reactions) at doses that do not exceed prednisone 20 mg per day or equivalent are permitted.

Localized hormonal or bone-sparing treatment for non-B-cell malignancies and localized radiotherapy for medical conditions other than the underlying B-cell malignancies may be considered if necessary. Palliative (ie, nontherapeutic) radiotherapy for control of DLBCL-related symptoms is allowed.

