3.1. Subject Inclusion Criteria

The following criteria are required for inclusion in the study:

1. Male or female, 18 years of age or older.
2. Histologically documented diagnosis of *de novo* DLBCL.
 - a. For Phase 1, subjects may have any DLBCL subtype.
 - b. For Phase 2, subjects must have ABC or unclassifiable subtypes of DLBCL confirmed by immunohistochemistry (IHC) using the Hans algorithm.

Subjects having a computed tomography (CT) scan abnormality with uncertain interpretation following completion of the most recent treatment regimen must have biopsy confirmation of residual DLBCL before study entry.

3. Relapsed or refractory DLBCL, defined as having received at least 1 but no more than 3 prior treatment regimens and ineligible for HDC/ASCT.
4. Fluorodeoxyglucose-avid disease (based on local evaluation) per the Lugano Classification ([Cheson et al 2014](#)). Fluorodeoxyglucose-avid disease is defined as disease with a 5-point scale (5PS) score of 4 or 5.
5. Subjects must have archived tumor tissue (block or 15-20 unstained slides) available, or be willing to undergo an incisional or excisional lymph node biopsy of accessible adenopathy (or, in less accessible lymph nodes, 4 to 8 core biopsies).
6. At least 1 measurable (≥ 2 cm in longest dimension) lesion on CT scan or magnetic resonance imaging (MRI).
7. Eastern Cooperative Oncology Group (ECOG) performance status 0 to 2.
8. Adequate bone marrow, renal, and hepatic function, per local reference laboratory ranges (values must not be achieved with growth factors) as follows:
 - a. ANC $\geq 1.5 \times 10^9/L$.
 - b. Platelet count $\geq 75 \times 10^9/L$.
 - c. Hemoglobin ≥ 8.0 g/dL (transfusions are permitted to achieve required hemoglobin level).
 - d. Serum creatinine ≤ 2.0 g/dL or measured or calculated creatinine clearance ≥ 30 mL/min by the Cockcroft-Gault Equation.

- e. Aspartate aminotransferase (AST) and ALT $\leq 2.5 \times$ institutional upper limit of normal (ULN) or $\leq 5 \times$ ULN for subjects with known hepatic metastases.
 - f. Total bilirubin $\leq 1.5 \times$ ULN if no liver metastases or $< 3 \times$ ULN in the presence of liver metastases or presence of documented Gilbert's syndrome (unconjugated hyperbilirubinemia). Further evaluation should be performed to confirm and document the origin of increase.
9. Prothrombin time (PT)/international normalized ratio (INR) $< 1.5 \times$ ULN and activated partial thromboplastin time (aPTT) $< 1.5 \times$ ULN.

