5.7.2. Prohibited Medications and Measures

The following medications are prohibited during the treatment:

- Any concurrent anticancer therapy (eg, chemotherapy, radiation therapy, surgery, immunotherapy, biologic therapy, hormonal therapy, or tumor embolization) other than those specified in the Protocol.
- Any investigational medication before withdrawing from the study.
- Corticosteroids for the treatment of the underlying malignancy.
- Potent inducers of CYP3A4.
- Warfarin or vitamin K antagonists.

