7.5.4. Response Criteria – the Lugano Classification

The Lugano Classification ([Cheson et al 2014](#)) will be used to assess response to treatment (see [Table 11](#)). As PET assessment is required to confirm CR or PR, PET-based response should be applied in most circumstances. Computed tomography/MRI-based response criteria are provided in the event that PET scans cannot be interpreted.

Table 11: Lugano Classification for Response Assessment

Site	PET-Based Response	CT-Based Response
	Complete metabolic response	Complete radiologic response (all of the following)
Lymph nodes and extralymphatic sites	Score 1, 2, or 3 with or without a residual mass on 5PS. ^a	Target nodes/nodal masses must regress to ≤ 1.5 cm in LDi.
Nonmeasured lesion	Not applicable.	Absent.
Organ enlargement	Not applicable.	Regress to normal.
New lesions	None.	None.
Bone marrow	No evidence of FDG-avid disease in marrow.	Normal by morphology; if indeterminate, IHC negative.
	Partial metabolic response	Partial remission (all of the following)
Lymph nodes and extralymphatic sites	
 • Score 4 or 5^a with reduced uptake compared with baseline and residual mass(es) of any size. • At interim, these findings suggest responding disease. • At EOT, these findings suggest residual disease. 	
 • ≥ 50% decrease in SPD of up to 6 target measurable nodes and extranodal sites. • When a lesion is too small to measure on CT, assign 5 mm × 5 mm as the default. • When no longer visible, 0 × 0 mm. 
For a node > 5 mm × 5 mm but smaller than normal, use actual measurement.

Nonmeasured lesions	Not applicable.	Absent/regressed, but no increase.
Organ enlargement	Not applicable.	Spleen must have regressed by > 50% in length beyond normal.
New lesions	None.	None.
Bone marrow	Residual uptake higher than uptake in normal marrow but reduced compared with baseline (diffuse uptake compatible with reactive changes from chemotherapy allowed). If there are persistent focal changes in the marrow in the context of a nodal response, consider further evaluation with MRI or biopsy.	Not applicable.

Table 11: Lugano Classification for Response Assessment (Continued)

Site	PET-Based Response	CT-Based Response
	No metabolic response	Stable disease

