9.4. Statistical Analyses

9.4.1. Primary Analyses

The primary endpoint is ORR; a subject will be considered as a responder if his or her best overall response is PR or better based on the Lugano Classification (Cheson et al 2014). The rate of responders will be estimated using the observed rate, and its 90% CI will be calculated using the method of Koyama and Chen (2008) that accounts for the early termination rules of the Simon 2-stage design. The study will be considered successful if the total number of objective responders is ≥ 29 in Phase 2.

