7.3. Analysis of the Primary Efficacy Parameter

7.3.1. Primary Efficacy Analysis

The primary variable for the Phase 2 of the study is ORR, which is defined as the proportion of subjects with best response (CR or PR) by modified Lugano Classification ([Cheson et al 2014](#)) for DLBCL. The proportion of responders within each treatment group will be estimated with 90% CIs by treatment group. Confidence intervals will be calculated based on the method of Koyama and Chen ([2008](#)) that accounts for early termination rules of the Simon 2-stage design. Within each treatment group, 1- sample binomial test will be used to test the null hypothesis.

In general, best response is determined on the subject level using the highest overall response achieved postbaseline. In the case of SD, measurements must meet the SD criteria at least once after study entry at a minimum interval of 56 days. Subjects who fail to meet these criteria will have best response of PD if the next available Lugano Classification evaluation after the initial scan indicates PD or NE if no additional evaluations are available.

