7.4.3. Progression-Free Survival

Progression-free survival is defined as the number of days from the date of first dose (which is not necessarily Day 1) to the earlier of death or disease progression. Date of death will be determined using the Death Report, the Survival Follow-Up, and the Subject Status eCRFs. Disease progression is measured by investigator assessment of objective radiographic disease assessments per Lugano Classification. Censoring for PFS will follow the algorithm outlined in Table 3, which is based on FDA guidance (FDA 2007). The analyses will be based on the ITT population, according to treatment assignment. Time-to-event data will be analyzed by the Kaplan-Meier method, treating subjects with no observed death or progression as censored at the last valid radiologic assessment visit. Median PFS and 90% CI will be estimated.

Table 3: Evaluation and Censoring of Progression-Free Survival

Situation	Outcome	Date of Progression or Censoring
No baseline tumor assessments	Censored	Date of enrollment
Progression documented between scheduled visits	Progressed	Earliest of: 
 • Date of radiological assessment showing new lesion (if progression is based on new lesion); or • Date of last radiological assessment of measured lesions (if progression is based on increase in sum of measured lesions)
No progression	Censored	Date of last valid radiologic assessment (not NE and not missing)
Treatment discontinuation for undocumented progression	Censored	Date of last valid radiologic assessment (not NE and not missing)
Treatment discontinuation for toxicity or other reason	Censored	Date of last valid radiologic assessment (not NE and not missing)
New anticancer treatment started	Censored	Date of last valid radiologic assessment (not NE and not missing)
Death before first pharmacodynamic assessment	Progressed	Date of death
Death between adequate assessment visits	Progressed	Date of death
Death or progression after more than 1 missed assessment	Censored	Date of last valid radiologic assessment (not NE and not missing)

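### Palliative radiotherapy to lymphoma sites is permitted on study, but the best-response rule behind the primary ORR does not say how responses after radiotherapy are handled

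*Protocol*

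**What the plan says.** Protocol 5.7 (Concomitant Medications): "Palliative (ie, nontherapeutic) radiotherapy for control of DLBCL-related symptoms is allowed". It sets no limit on timing or on whether the irradiated site is a target lesion. Protocol 5.7.2 prohibits "Any concurrent anticancer therapy (eg, chemotherapy, radiation therapy, surgery, immunotherapy, biologic therapy, hormonal therapy, or tumor embolization) other than those specified in the Protocol"; the closing exemption covers the radiotherapy that 5.7 permits.

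On the endpoint, Protocol 9.4.1 says that "a subject will be considered as a responder if his or her best overall response is PR or better based on the Lugano Classification". SAP 7.3.1 adds, as a general rule, that "best response is determined on the subject level using the highest overall response achieved postbaseline".

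Protocol Table 11 gives two routes to PR. On CT it needs "≥ 50% decrease in SPD of up to 6 target measurable nodes and extranodal sites", together with conditions on nonmeasured lesions, spleen and new lesions. On PET it needs a score of 4 or 5 "with reduced uptake compared with baseline and residual mass(es) of any size". Neither route mentions irradiated sites. Inclusion criterion 6 requires only one measurable lesion.

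SAP Table 3 censors PFS under "New anticancer treatment started". SAP 7.3.1 has no corresponding entry for ORR.

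**The concern.** Radiotherapy can shrink a lesion or reduce its FDG uptake whatever the study drugs do. If the irradiated lesion is the only target, or dominates the sum of products, the subject can meet PR and be counted as a responder to INCB039110 plus ibrutinib. The protocol and SAP describe no central response review that could apply a common rule, and SAP Appendix B lists response as investigator response. The per-protocol analysis does not remove such a subject on this ground, because permitted radiotherapy is not a violation.

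Phase 2 is a single-group trial decided by one count, 29 or more responders of 60, so a small number of misattributed responses matters.

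**Working it through.** **Is the route open in the text?**

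1. Radiotherapy to a DLBCL site is permitted on study (Protocol 5.7) and exempt from the ban (5.7.2).
2. The irradiated lesion may be the only measured one (inclusion criterion 6).
3. Table 11 does not exclude it from the response calculation.
4. SAP 7.3.1 stops best response neither at radiotherapy nor at new anticancer therapy.
5. Radiotherapy may also fall between the baseline scan and Day 1. The scan may be up to 28 days old (Protocol 7.5.1 and 7.5.2), while exclusion criterion 25 requires a 2-week gap, or 1 week for palliative radiation with approval.

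I found no rule that closes this route.

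**Reproducing the design.** Inputs from Protocol 9.2.2, 9.3 and 9.4.1: p0 = 0.40, p1 = 0.55, 1-sided alpha 0.10, power 80%, stop at 9 or fewer of 22, success at 29 or more of 60. The exact probability of success at true rate p is

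P(p) = sum over x = 10 to 22 of Bin(x; 22, p) × P[Bin(38, p) ≥ 29 − x]

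- P(0.40) = 0.0949, within the 0.10 limit.
- P(0.55) = 0.8004, matching the stated 80%.

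**Sensitivity to an uplift (assumed).** Suppose the true drug response rate is 40% and radiation adds u points to the observed rate in both stages. Expected extra responders are 60 × u. The implied share of non-responders misclassified is u / 0.60.

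| Uplift u | Observed rate | Extra responders in 60 | Share of non-responders | Type I error |
|---|---|---|---|---|
| 0 | 40% | 0 | 0 | 0.0949 |
| 1 point | 41% | 0.6 | 1.7% | 0.1234 |
| 2 points | 42% | 1.2 | 3.3% | 0.1571 |
| 3 points | 43% | 1.8 | 5.0% | 0.1960 |

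If instead exactly one false responder affects only the final count, so that 28 true responders suffice, the error is 0.134. With two it is 0.178, and with three 0.224.

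**Cost of a strict rule (assumed).** If a fraction f of true responders at 55% become non-responders because radiotherapy preceded their first documented response, the observed rate is 0.55 × (1 − f).

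| f | Observed rate | Power |
|---|---|---|
| 0 | 55.0% | 0.800 |
| 2% | 53.9% | 0.757 |
| 5% | 52.25% | 0.682 |
| 10% | 49.5% | 0.536 |

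**The case against.** The strongest reply is that the route is narrow.

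- The permitted radiotherapy is labelled nontherapeutic; radiation given to treat the lymphoma would be a deviation.
- Radiographic progression forces withdrawal from treatment (Protocol 5.6.1).
- After discontinuation for other reasons, scheduled imaging runs only to progression or new anticancer therapy (Protocol 7.5.1).
- Treatment is expected to last about 4 months, with scans at Weeks 8 and 16, so there is little time for radiotherapy before progression.
- Table 11 judges all disease. With several sites, irradiating one is less likely to produce an overall response.

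Most of this stands, and it limits how often the problem can arise. It does not close the gap. The nontherapeutic label describes intent and does not keep the field off a target lesion. Neither document says that palliative radiotherapy counts as new anticancer therapy, and SAP 7.3.1 does not stop best response at progression or discontinuation.

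Two stronger readings are tempting. A reader might infer that the ORR is biased upward. The documents do not show this: they give neither the frequency of palliative radiotherapy nor the rate at which it turns a non-responder into an overall responder. A reader might also infer that PFS is protected where ORR is not. SAP Table 3 does not say whether palliative radiotherapy counts as new anticancer treatment, so PFS may have no radiotherapy rule either.

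**Conclusion.** The gap is real. Followed as written, the plan could credit a radiation-induced response to the drugs and count it toward the threshold of 29. The risk is greatest with one or few measurable lesions, or under the PET PR criterion, which has no size threshold.

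The size is unknown. The error rates of 0.123 to 0.196 show how any misclassification of that amount would act on this design; they are not estimates of what radiotherapy would do. They assume a true rate of 40% and the same uplift in both stages. They do show little slack: a 1-point uplift, 0.6 expected subjects in 60, takes the error above the planned 0.10. That justifies a written rule, but not a claim that the result will be biased.

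**What to change.** These are analysis changes only; whether radiotherapy is allowed is untouched.

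1. In SAP 7.3.1, for the primary ORR analysis, count a CR or PR only if it is first documented before any radiotherapy to a DLBCL lesion given after the baseline scan, and before any new anticancer therapy. Starting the clock at the baseline scan avoids penalising radiotherapy completed before it and covers the interval up to Day 1.
2. Count a response first seen after such radiotherapy only if the irradiated site is recorded and the response criteria are met on non-irradiated target lesions. Otherwise classify the subject as a non-responder.
3. Report ORR under the current rule, using all postbaseline assessments, as a sensitivity analysis.
4. State in SAP Table 3 whether palliative radiotherapy counts as new anticancer treatment.

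The cost is a short SAP amendment, a date check, and lesion-level review for any irradiated subject. Protocol 5.7 and 7.3.2 require treatments and procedures to be recorded, but the documents do not confirm that the eCRF captures the irradiated site; check this first. Some true responses may be lost, with power about 0.757 if 2% of true responders are reclassified. The second limb limits that loss, and the sensitivity analysis shows its effect.
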